8.4.4 Risk-Benefit Assessment

The potential risks associated with study procedures are minimal. Results gathered from this study will provide preliminary information on the effects of the patient navigation intervention on use of mental health services and suicidal ideation and behavior. This information can be used in subsequent studies to test the effectiveness and implementation of this intervention. Given the minimal risk nature of the study, the risks are considered reasonable in relation to the generalizable knowledge to be gained.

8.5 Recruitment Strategy

For qualitative interviews, potential participants identified through any of the three avenues by clinicians, behavioral health screening and by diagnostic codes in CHOP ED. Academic Associates who work in the CHOP ED and study staff will confirm eligibility for the study, describe the study procedures, and enroll interested participants. Academic Associates will notify study staff of the enrollment. Study staff will contact participants and schedule interviews.

For field testing and RCT, potential participants will be identified through any of the three avenues by clinicians, behavioral health screening and by diagnostic codes in CHOP ED. Academic Associates who work in the CHOP ED and study staff will confirm eligibility for the study, describe the study procedures, and enroll interested participants. Academic associates will notify study staff of the enrollment. Study staff will contact participants and schedule study visit 1 (intervention session for field testing and baseline assessment for RCT). For the RCT, a study flyer will be given to families who are undecided about the study or do not have time to be enrolled in the ED

All recruitment materials will be IRB approved.

8.6 Informed Consent/Accent and HIPAA Authorization

Parent/legal guardian consent and child assent will be obtained for study participation. Consent will may be collected in-person or remotely and may be documented on paper or electronically. A waiver of screening consent is being requested to screen medical records for inclusion/exclusion. For the qualitative interviews, for youth age 18 years, consent will be attained. If a youth turns 18 during the course of the study, consent will be gathered by the currently approved consent form for continued participation at the next study visit or contact after the youth reaches the age of majority. For youth between 10-17 years of age, youth assent and parental/ legal guardian consent will be attained. For the field testing and RCT, for youth ages 14 years or older, consent will be attained. If a youth turns 14 during the course of the study, consent will be gathered by the currently approved consent form for continued participation at the next study visit or contact after the youth reaches the age of majority. For youth between 10-13 years of age, youth assent and parental/ legal guardian consent will be attained. Participation in the study will be completely voluntary, and participants will have the study rationale and goals explained to them, as well as the requirements for participation, the risks and benefits of participation, and alternatives to participation. This is done by reviewing verbally and participants will be allowed to ask questions and state concerns. Should any participant become intolerant of any aspect of the study or an exclusionary condition be identified, their participation will be discontinued. If potential participants want additional time to consider study participation, they can be contacted at a later time by study staff to consent. There is no time limit for consent and participation as long as that phase of the study is still active. Parent consent and child assent also will be gathered for the qualitative interview consent form for their willingness to participate in the field testing study procedures. If consent is gathered in person, research staff will be given a hard copy of the signed consent form. In the event that the participants are not seen in person, an alternative method of obtaining informed consent will be used. Eligible participants will be sent the informed consent document electronically through REDCap. The study team will then go over the document in detail with the eligible parents/legal guardians and youth. The e-consent function in REDCap will be used to obtain the parent/legal guardian's signature. The signed e-consent will then be stored within REDCap, and a copy of the form will be available to download and emailed securely to the family.

Verbal Consent from patient navigators

Informed Consent of patient navigators will be obtained verbally. The aforementioned patient navigators are employed at CHOP and will not be paid for their participation as a secondary research participant. A waiver of documentation of consent is being requested for these participants. Verbal consent will be documented internally by the study team using a Consent Affirmation Note. Informed consent will be conducted by a study team member (other than a principal investigator) so that the patient navigators does not feel pressure to be a secondary research participant. The provider will have no direct reporting relationship to the study team member that obtains informed consent from them. Those noted are research study team members as well as secondary research subjects. They will be provided with a verbal consent form outlining what their participation as a research subject will entail. Participation will include the completion of surveys of feasibility and acceptability of the intervention and the completion of fidelity checklists. Completion of fidelity checklists is a widely accepted, standard practice in the delivery of a behavioral intervention to monitor adherence to an intervention manual and part of routine practice at CHOP. These checklists will be used in the clinical supervision of the patient navigator and for research purposes. However, participants can choose to not have their fidelity checklist data used beyond clinical supervision purposes (i.e., for research purposes). Participants will be given time to ask questions and make an informed decision regarding their completion of the feasibility and satisfaction surveys and use of the “data” from the fidelity checklists for research purposes. No HIPAA related information will be gathered from the patient navigators.

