The study will recruit from CHOP pediatric hospital ED with a total of 151 participants (75 youth, 75 caregivers, and 1 patient navigator). Eligible youth will identify as Black, be between the ages of 10-18, have recent or past suicidal ideation or behaviors and are not currently receiving mental health treatment. Caregivers are parents or legal guardians of eligible youth. Patient navigator will be hired patient navigator who consents to being a secondary research participant. Study procedures may be conducted in-person, over the phone, or online.

[figure not shown]
Study Interventions and Measures:

Participants will be randomized to the adapted STAT-ED or enhanced Treatment as Usual which will consist of follow up telephone contacts following discharge from the ED. Main RCT study outcomes are mental health treatment initiation and suicidal ideation.

Table 1: Schedule of Study Procedures for Randomized Controlled Trial

Study Phase	Screening	Observation Study Visits		
Visit Number		Baseline	2 month follow up	6 month follow up
Informed Consent/Assent	X			
Review Inclusion/Exclusion Criteria	X	X		
MYST		X	X	X
SIQ-Jr		X	X	X
Demographics		X		
PANAS		X		
AIM			X	X
ED STARS			X	X
Adverse Event / Unanticipated Problems Assessment		X	X	X

Figure 1: Flow Diagram for RCT

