3.4.2 Exclusion Criteria

- 1) Does not identify Black as one of their races
- 2) Under 10 or over 18 years old
- 3) Does not speak English
- 4) No history of suicidal ideation or behavior

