3.4.2.3 Youth Exclusion criteria for RCT

- 1) Exclusion criteria listed in section 3.4.2
- 2) Currently engaged in mental health treatment

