3.4.2.4 Patient Navigator Exclusion Criteria

- 1) Does not consent to be a secondary research participant

Subjects with limited English proficiency will be excluded from this study because the interview materials and measures are not available in multiple languages. In addition, the adaptation and implementation of the intervention in multiple languages is not feasible for this pilot study. If this study shows efficacy, we will hope to be able to engage Black families who speak languages other than English in the next study.

Subjects that do not meet all of the enrollment criteria may not be enrolled. Any violations of these criteria must be reported in accordance with IRB Policies and Procedures.

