5.2 Efficacy Evaluations

In the RCT, these are the measures that will be used to assess efficacy (mental health utilization)- ED STARS. The three primary efficacy outcomes are 1) whether the patient initiated mental health treatment (yes/no), 2) time to treatment initiation, and 3) number of

treatment sessions attended. Other outcomes are suicidal ideation and behavior measured by SIQ-Jr.

5.2.1 Diagnostic Tests, Scales, Measures, etc.

In the qualitative interviews, the research staff will conduct semi-structured interviews with questions concerning perceptions and preferences of mental health treatment and barriers and facilitators to accessing mental health services with youth and caregiver participants. In the field testing, participants will not complete any measures or scales. . In the RCT, ED STARS is an interview and will be administered by research staff to caregivers at 2 (Study visit 2) and 6 months (final visit) after baseline assessment. SIQ-Jr is a self-report measure that will be administered to youth at baseline and 2 and 6 months after baseline assessments.

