6 STATISTICAL CONSIDERATIONS

6.1 Primary Endpoint

Primary endpoint for qualitative phase (interviews and field testing): themes of caregiver and youth mental health attitudes and engagement and an adapted STAT-ED manual
Primary endpoint for randomized trial: mental health treatment initiation. The three primary efficacy outcomes are: a) whether the patient initiated mental health treatment (yes/no), b) time to treatment initiation, and c) number of treatment sessions attended.

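### Section 8.6 discontinues anyone found to have an exclusion, with no cut-off at randomisation, and needs reconciling with the RCT's exclusion for current treatment, its follow-up and its analysis

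*Combined protocol and SAP*

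**What the plan says.** The consent section (8.6), which covers the interviews, the field testing and the RCT, contains this sentence: "Should any participant become intolerant of any aspect of the study or an exclusionary condition be identified, their participation will be discontinued". It is mandatory and carries no time limit.

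The second RCT exclusion for youth (section 3.4.2.3) is "Currently engaged in mental health treatment". Section 6.1 gives "Primary endpoint for randomized trial: mental health treatment initiation" and lists three primary outcomes: "whether the patient initiated mental health treatment (yes/no), b) time to treatment initiation, and c) number of treatment sessions attended".

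Other parts of the protocol bear on how the sentence should be read:

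- **Entry.** The closing paragraph under section 3.4.2.4 says "Subjects that do not meet all of the enrollment criteria may not be enrolled". In Table 1 the row "Review Inclusion/Exclusion Criteria" is marked at screening and baseline only. Section 4.2.1 lists the review ahead of randomisation.
- **Follow-up.** Under section 5.2.1 the ED STARS interview "will be administered by research staff to caregivers at 2 (Study visit 2) and 6 months (final visit) after baseline assessment", with no exception for youth who have started care. SIQ-Jr follows the same visits. Section 3.1.2 compares session counts at both follow-up points.
- **Withdrawal.** Section 4.4 gives discretionary reasons for withdrawal, and starting treatment is not among them. Section 4.4.1 still asks for post-intervention assessments from subjects who leave ahead of the intervention or while it is under way.
- **End of intervention.** Section 1.2 expects the adapted STAT-ED to run up to the first mental health appointment.
- **Analysis.** Section 6 defines no analysis population and does not say that youth are analysed in the arm to which they were assigned.

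**The concern.** The trial tries to bring about a status that its own exclusion list names. A youth who starts care and stays in it comes to meet section 3.4.2.3, and section 8.6 then says participation ends. Yet the third primary outcome, sessions attended, accrues only after care has started, and the 6-month SIQ-Jr is needed from everyone.

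A narrower reading, that section 8.6 concerns ineligibility that existed at entry but was missed, avoids that clash but still removes youth after randomisation. Late discovery is realistic:

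- Chart review does not reach protected mental health records (sections 4.2 and 5.1.1).
- ED STARS service use is first asked at month 2 (Table 1).
- Records are reviewed again at Visit 2 (section 4.2.2).

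Discovery could also depend on arm. STAT-ED families have one or two contacts a week and help with appointments (section 1.2). Control families get telephone check-ins whose frequency is not stated (section 3.1.2). If removal depends on arm, the groups being compared are no longer the groups that were randomised. Section 6.4 says the pilot's effect sizes will feed the sample size of the next trial.

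**Working it through.** **Step 1: the text side by side.** The first half of the section 8.6 sentence concerns people already in the study, since only they can come to find some aspect of it intolerable, and only existing participation can be discontinued. So the sentence reaches enrolled participants. For exclusions, however, it speaks of a condition being identified, which fits late discovery better than a new event. Being currently in treatment is a status assessed at eligibility review, whereas initiating treatment is a later event. The two overlap in time but are not the same thing.

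**Step 2: whether section 4.4.1 closes the gap.** It does so in part. It covers subjects withdrawn up to and including the intervention period. Section 1.2 ends the STAT-ED intervention at about the first appointment, so a youth removed for having started care is at or past that end and is not clearly covered. A youth found ineligible while navigation is still under way probably is covered. One found through the month-2 interview, after navigation has ended, is not clearly covered.

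**Step 3: the plan's own retention figure.** Section 3.3.2 expects 85 evaluable subjects from 100: 100 × (1 − 0.15) = 85, which agrees with the 15% in section 6.4. These are individuals in 50 dyads. The allowance is not split by reason, so it does not show whether rule-driven removals were foreseen.

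**Step 4: the literal reading, for direction only.** Assume 25 youth per arm and no data after discontinuation. The documents give no initiation rates, so a range is shown. Youth remaining = 25 × (1 − initiation rate).

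| Assumed initiation, control / STAT-ED | Remaining, control | Remaining, STAT-ED |
|---|---|---|
| 20% / 40% | 25 × 0.80 = 20 | 25 × 0.60 = 15 |
| 30% / 60% | 25 × 0.70 = 17.5 | 25 × 0.40 = 10 |
| 50% / 80% | 25 × 0.50 = 12.5 | 25 × 0.20 = 5 |

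For session counts, assume 60% STAT-ED v 35% control and 6 sessions per initiator. The means are 0.60 × 6 = 3.6 and 0.35 × 6 = 2.1, a difference of 1.5. If counting stopped at the first session they would be 0.60 and 0.35, a difference of 0.25. Initiation (yes/no) and time to initiation would still be known.

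**Step 5: the narrower reading, for direction only.** Assume 25 per arm, 10% (2.5 youth) already in care at entry, and 40% true initiation among the other 22.5 in both arms. Youth already in care count as initiators if they go undetected. With k undetected youth left in an arm, observed initiation = (22.5 × 0.40 + k) / (22.5 + k).

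- **Detection 80% STAT-ED, 40% control.** k = 0.5 and 1.5. Initiation is 9.5/23 = 41.3% v 10.5/24 = 43.75%, a difference of −2.4 points with no true effect. That is about 0.024 × 25 = 0.6 of a youth.
- **Extreme case, 100% v 0%.** 9/22.5 = 40% v 11.5/25 = 46%, a difference of −6 points.
- **Equal detection, 40% in both.** 43.75% in both, difference 0.
- **No removal.** 11.5/25 = 46% in both, difference 0.

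The standard error of the difference in the first case is √(0.413 × 0.587/23 + 0.4375 × 0.5625/24) = √(0.01054 + 0.01025) = 0.144, or about 14 points.

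**The case against.** The strongest reply is that the sentence should not be read alone. The criteria govern enrolment, no visit after baseline re-applies them, starting care is not a listed reason for withdrawal, and the design plainly needs treatment starters at 2 and 6 months. The sentence sits among consent provisions and looks like an eligibility safeguard. This stands. A reader might infer that youth leave the study at the moment they succeed and that only non-initiators reach month 6. The documents do not support that as the operating rule, and section 4.4.1 undercuts the assumption of total data loss.

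A reader might also infer from the exclusion "Under 10 or over 18 years old" that an 18-year-old who turns 19 must leave. That is weak. It is an entry criterion, and section 8.6 itself handles the ages it does mention, 14 and 18, by obtaining consent to continue rather than by removal.

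Differential discovery is plausible rather than shown. One social worker delivers both conditions, controls are also telephoned, and chart review is not specific to an arm. On the assumed inputs the bias is small beside the sampling error of a pilot that section 6.4 says is not meant to detect significant differences. All this limits the weight of the point.

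The reply does not supply the missing cut-off at randomisation. The discretionary list in section 4.4 does not override a mandatory sentence, and nothing in section 6 says how a removed youth is analysed.

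**Conclusion.** The point holds as a conflict of wording with a modest statistical consequence. Section 8.6 states a rule without a time limit that, read literally, is incompatible with following treatment starters to 6 months. Read as the rest of the protocol suggests, it still takes randomised youth out of the study when an exclusion surfaces late. Follow-up after the intervention ends and analysis by assigned arm are not secured elsewhere.

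Severity is minor to moderate. Routine loss of treatment starters is unlikely, and no loss of outcome data has been demonstrated. All rates, session counts and detection probabilities in the working are assumptions, as is the equal split of 50 youth. They show the direction of the effect and not its likely size. The conclusion that late removal can unbalance the arms needs only that some youth are found ineligible after randomisation and that discovery differs by arm. With equal discovery, the illustrated bias is zero.

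**What to change.** Reconcile section 8.6 with sections 3.4.2.3, 4.4, 4.4.1 and 5.2.1 by stating that:

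- eligibility criteria are applied up to randomisation;
- after randomisation, neither starting mental health treatment nor late discovery of an exclusion ends the scheduled 2- and 6-month outcome assessments;
- all randomised youth are analysed in the arm to which they were assigned (add this to section 6.3.2);
- optionally, a sensitivity analysis drops youth shown to be ineligible by information dated before randomisation.

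Withdrawal at a participant's request and withdrawal for safety stay as they are. The change concerns outcome assessment and analysis only. It does not address whether navigation continues for a youth found ineligible.

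The cost is a short amendment. No visits or staff are added, because the assessments are already scheduled. The downside is that a few ineligible youth stay in the main analysis. In the illustration this raises observed initiation from 40% to 46% in both arms but leaves the difference unbiased. The sensitivity analysis shows how much those youth matter.

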8.7 Payment to Subjects/Families

8.7.1 Reimbursement for travel, parking and meals

We will provide transportation services for each family to complete study visits if conducted in person.

8.7.2 Payments to subject for time, effort and inconvenience (i.e. compensation)

For qualitative interviews, \$30 for each participant which includes both youth and caregiver. For field testing, \$25 for each subject. For randomized trial: \$25 for baseline, \$25 for 2 month follow up and \$50 for 6-month follow up for each subject.

9 PUBLICATION

The study protocol for this application will be registered with Clinicaltrials.gov. Results will be submitted to Clinicaltrials.gov after completion and analysis of data. Informed consent documents will include a specific statement regarding the dissemination of aggregate study results in Clinicaltrials.gov, peer-reviewed publications, and other policy-relevant summaries. The study team plans to work closely with the Penn INSPIRE center to disseminate and implement the findings of the research study into accessible and usable formats in research, clinical, and community-based settings. Using social media, policy briefs, mass emails and newsletters, we will target findings to city, state and national

policymakers, county behavioral health departments across the state of Pennsylvania, and pediatric emergency departments. We will also work with PolicyLab at CHOP to develop dissemination plans. PolicyLab has extensive experience distilling research findings into policy-relevant summaries and disseminating research findings to end-users. We will also utilize traditional approaches such as peer-reviewed publications and presentations at national meetings to disseminate findings to other researchers.

APPENDIX

See attached.
